6.2.2.4. Medicated Topical Background Therapy-Free days

- Definition: days where a subject maintains a response of EASI-90 or greater without the use of medicated topical background therapy
 - For subjects discontinued from the study or received rescue therapy the medicated background free days are 0.
 - For other subjects, during the treatment period from Day 1 up and including last day of treatment exposure, days between two consecutive EASI-90 response without the use of medicated topical background therapy are counted.
- Analysis set: FAS (Section 4).
- Analysis methodology: ANCOVA (Section 5.2.3).
- Number of participants, least square mean (LSM) along with the corresponding 95% confidence interval will be presented for each treatment arm.
- The LSM difference along with the corresponding p-value and 95% confidence interval will be presented for abrocitinib versus dupilumab.

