4.4. End of Study Definition

A participant is considered to have completed the study if he/she has completed all phases of the study including the last visit or the last scheduled procedure shown in the [Schedule of Activities](#).

The end of the study is defined as the date of the last visit of the last participant in the study or last scheduled procedure shown in the [Schedule of Activities](#) for the last participant in the trial globally.

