7. DISCONTINUATION OF STUDY INTERVENTION AND PARTICIPANT DISCONTINUATION/WITHDRAWAL

7.1. Discontinuation of Study Intervention

In certain instances, it may be necessary for a participant to permanently discontinue study intervention. Per the study estimands, if study intervention is permanently discontinued, the participant will remain in the study to be evaluated for EOT assessments (as per the Schedule of Activities) (See Section 6.5.2).

If a participant has a clinically significant, treatment-emergent, abnormality at the time of withdrawal from the study, the Pfizer Medical Monitor (or designee) should be notified and every effort should be made to arrange follow-up evaluations at appropriate intervals to document the course of the abnormality. All abnormal laboratory events of clinical significance should be followed until the laboratory values have returned to normal or baseline levels or are deemed clinically stable. Follow-up for abnormal laboratory findings and adverse events by the investigator is required until the event or its sequelae resolve or stabilize at a level acceptable to the investigator, and Pfizer concurs with that assessment. Note that discontinuation of study treatment does not represent withdrawal from the study. Refer to [Appendix 11](#) for discontinuation criteria.

Refer to the [Schedule of Activities](#) for data to be collected at the time of intervention discontinuation and follow-up and for any further evaluations that need to be completed.

Discontinuation of study intervention for abnormal liver function should be considered by the investigator when a participant meets one of the conditions outlined in [Appendix 6](#) or if the investigator believes that it is in best interest of the participant.

If a clinically significant finding is identified (including, but not limited to changes from baseline in Fridericia-corrected Q wave interval [QTcF]) after enrollment, the investigator or qualified designee will determine if the participant can continue in the study and if any change in participant management is needed. This review of the ECG printed at the time of collection must be documented. Any new clinically relevant finding should be reported as an AE. Refer to [Appendix 8](#) for ECG values of potential clinical concern.

See the [SoA](#) for data to be collected at the time of intervention discontinuation and follow-up and for any further evaluations that need to be completed.

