reasons, or the inability of the participant to comply with the protocol-required schedule of study visits or procedures at a given study site. Participants that discontinue study intervention will remain in the study and must have their end of treatment visit within 1 week after their last dose and will then enter the 4-week follow-up period. Refer to [Appendix 11](#) for guidelines for monitoring and discontinuation.

If the participant withdraws from the study, and also withdraws consent for disclosure of future information, no further evaluations should be performed, and no additional data should be collected. The sponsor may retain and continue to use any data collected before such withdrawal of consent.

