Endpoint	Analysis Type	Population	Data Inclusion and Rules for Handling Intercurrent Events and Missing Data	Analysis Model
improvement in the severity of PP-NRS scale		PP-NRS ≥ 4	experienced the event, their time to event will be right censored at the last available measurement time.	
Medicated Topical Background Therapy-Free days	Main analysis	FAS	The intercurrent event is captured through endpoint definition. Missing dates will be imputed by Pfizer standards.	ANCOVA

CMH=Cochran-Mantel-Haenszel; ANCOVA=Analysis of Covariance; MMRM=Mixed-effect Model Repeated Measures; TP=Tipping Point.

PP-NRS4 Response at all other scheduled timepoints will follow the main analysis of Week 2 PP-NRS4 Response. Other binary endpoints will follow the main analysis of Week 4 EASI-90 Response.

Other percent change from baseline or change from baseline to each specific post baseline scheduled time points in a continuous outcome measure will follow the main analysis of Weeks 2, 4, 8, 12, 16, 20 and 26 Percent Change from Baseline in %BSA.

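### The zero rule for medicated topical background therapy-free days follows study status and has no end date, so an event after Week 26 can erase a completed treatment course while an early treatment stopper keeps days

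*SAP*

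**What the plan says.** SAP 6.2.2.4 defines the endpoint in two branches.

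- Zero branch: "For subjects discontinued from the study or received rescue therapy the medicated background free days are 0".
- Counting branch: "For other subjects, during the treatment period from Day 1 up and including last day of treatment exposure", the "days between two consecutive EASI-90 response without the use of medicated topical background therapy are counted".

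SAP Appendix 1 adds no separate rule for this endpoint; it says only "The intercurrent event is captured through endpoint definition". SAP Appendix 8.1.4 reuses the definition with EASI-75 in place of EASI-90.

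The protocol treats treatment status and study status as different things. Section 7.1: "Note that discontinuation of study treatment does not represent withdrawal from the study". Section 7.3: "Participants that discontinue study intervention will remain in the study and must have their end of treatment visit within 1 week" of the last dose, after which they enter the 4-week follow-up. Section 6.1.1 gives the same 4-week period to everyone who does not enter the extension study. Under Section 4.4 a participant counts as a completer once "he/she has completed all phases of the study including the last visit" or last scheduled procedure.

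**The concern.** The two branches use different clocks. The count stops at the last day of treatment exposure. The zero trigger depends on study status and on any rescue, with no end date, so it can act after counting has closed.

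Two consequences follow from the text.

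- A participant who finishes 26 weeks, does not enter the extension and is lost before the Week 30 visit is discontinued from the study and scores 0. The same applies to one who is first rescued during follow-up. Protocol 6.5.1 classes other locally approved AD treatments as rescue, 6.5.2 gives a start (after Week 4) but no end, and concomitant treatments are still reviewed at Week 30.
- A participant who permanently stops treatment early, is not rescued, and attends the end-of-treatment and follow-up visits has not left the study. That participant falls in the counting branch and keeps the days earned.

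An endpoint about topical-free control on treatment then depends partly on attendance and treatment after drug has stopped. The SAP reports a least-squares mean difference, confidence interval and p-value for it.

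**Working it through.** The plan states no figure for this endpoint, so there is none to reproduce. The check applies the rule literally to constructed participants and then bounds the effect on an arm mean.

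**Inputs.** Visit days are 15, 29, 57, 85, 113, 141 and 183 (protocol Schedule of Activities; SAP Appendix 2). Assumptions: EASI-90 is met at every visit from Day 29; medicated topical is used through Day 36 and not after; each interval between responses runs from its first visit to the day before the next.

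**Worked cases.** For the completer, Days 29 to 182 are 154 days, less the 8 topical days (29 to 36), giving 154 − 8 = 146. For the participant who stops on Day 57 with an end-of-treatment visit on Day 64, Days 29 to 57 are 29 days, giving 29 − 8 = 21.

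| Participant | Rule as written | With the fix below |
|---|---|---|
| Completes 26 weeks, no event | 146 | 146 |
| Completes 26 weeks, withdraws Day 190 in follow-up | 0 | 146 |
| Completes 26 weeks, topical rescue on Day 170 | 0 | 0 |
| Stops treatment Day 57, attends end-of-treatment and follow-up | 21 | 0 |
| Same, but also withdraws from the study | 0 | 0 |

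Rows 1 and 2 have identical on-treatment data. So do rows 4 and 5. In each pair the score changes only because of study status.

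**Ceiling on the arm mean.** If everyone wrongly zeroed were a sustained responder using no medicated topical:

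- response from Week 2: 183 − 15 = 168 days, so 1% × 168 ≈ 1.7 days;
- response from Week 8: 183 − 57 = 126 days, so 1% × 126 ≈ 1.3 days.

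**Value under the protocol's assumed rates.** Protocol 9.2 assumes EASI-90 rates for dupilumab of 12% (Week 4) and 43% (Week 16). For abrocitinib it assumes 53% at Week 16, and 12% + 15% = 27% at Week 4. Taking 0 at Day 15, linear change between stated rates and a plateau after Week 16, mean EASI-90 days per participant are:

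- dupilumab: 14 × 0.12/2 + 84 × (0.12 + 0.43)/2 + 70 × 0.43 = 0.84 + 23.1 + 30.1 ≈ 54;
- abrocitinib: 14 × 0.27/2 + 84 × (0.27 + 0.53)/2 + 70 × 0.53 = 1.89 + 33.6 + 37.1 ≈ 73.

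If those zeroed are typical of their arm, each 1% costs about 0.5 days (dupilumab) or 0.7 days (abrocitinib), before topical-use days are subtracted.

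**The case against.** **Zeroing is a deliberate composite choice.** SAP Appendix 1 places the intercurrent event inside the endpoint definition, and scoring on-treatment rescue or dropout as complete failure of topical-free control is defensible. This stands. A reader might infer that erasing days earned before an on-treatment event is itself an error, because Estimand 1 applies non-response only after the event. The documents do not support that: SAP Section 4 states its general handling as a default that specific text may override, and 6.2.2.4 does so. The choice does not explain zeroing for events after the counting window has closed.

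**The treatment period is implied.** Estimands 1 and 2 limit dropout and rescue to the treatment period, and the counting bullet uses that term. The sponsor may have meant the same limit here, but the zero bullet does not contain it and would not be programmed that way from its words.

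**The two examples need different meanings of leaving the study.** If missing the last visit makes the completer a non-completer under protocol 4.4, the early stopper might seem to be one too. But the early stopper attends the follow-up visit as the last scheduled visit, and 7.1 and 7.3 keep that person in the study. What stands is that the SAP does not define discontinuation from the study for this endpoint. If it was meant to include stopping treatment, the early stopper would score 0, but the missing end date would remain. Nor does every early stopper keep credit: those withdrawn from the study, for example after unblinding (protocol 6.3.2), score 0.

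**The ceiling is far from typical.** This stands. Protocol 6.5.1 requires topical corticosteroid on active lesions from Day 1 and for 7 days after control, so 168 days is barely reachable.

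**Conclusion.** The rule as written gives wrong results for a definable group: participants who complete treatment, do not enter the extension, and then withdraw or are first rescued in the 4-week follow-up. It also scores treatment-only stoppers by a different standard from participants who leave the study, with no stated reason.

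The size is modest. Each 1% of an arm wrongly zeroed lowers its mean by at most about 1.3 to 1.7 days, if all are sustained and topical-free responders. Under the assumed EASI-90 rates, with the linear and plateau assumptions and typical participants, it is about 0.5 to 0.7 days, and less once topical-use days are removed. If those zeroed respond better than their arm's average, the value moves towards the ceiling.

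A reader might infer a bias in favour of one arm from different off-drug flare rates for a daily tablet and a two-weekly injection. The documents give no flare, rescue, follow-up loss or extension-entry rates by arm, so neither the direction nor the size of a between-arm effect can be determined.

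The endpoint is secondary and outside the testing sequence in SAP 5.1, and SAP 5.2 allows no significance claim for it. Primary and key secondary results are unaffected. The correction is still worth making before database lock.

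**What to change.** Replace the zero bullet in SAP 6.2.2.4 with:

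> For participants who permanently discontinue study intervention or withdraw from the study before completing the treatment period (Week 26), or who receive rescue therapy on or before the last day of treatment exposure, the days are 0. Withdrawal or rescue after the end of treatment does not change the count.

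State that the same wording applies to the EASI-75 version in Appendix 8.1.4.

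Whether days earned before an on-treatment event are kept or set to 0 is for the sponsor to decide; the wording above retains 0. Counting days up to the event can be added as a sensitivity analysis. In the worked cases that count would give 133 days for the Day 170 rescue and 21 for the Day 57 stopper.

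The cost is one SAP sentence and minor programming. No new data are needed.

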6.3. Other Endpoint(s)

Not applicable.

6.4. Subset Analyses

Summary statistics for the primary and key secondary endpoints will be presented by subgroups below.

- Age (years) group (<40, ≥40; <65, ≥65);
- Sex (Male, Female);
- Race (White, Black or African-American, Asian, Other);¹
- Region of enrollment (US/Canada/Australia, Europe, Asia);
- Weight (kg) (<70, 70 to 100, >100 kg);
- AD Duration (years) group (<26, ≥26);
- Baseline disease severity (moderate, severe);
- Baseline EASI group (16-25, >25);
- Baseline % BSA group (10-30, >30-50, >50);
- Previous cyclosporine exposure (cyclosporine naïve, cyclosporine exposed);
- Prior AD medications (topical agents only, systemic agents)

Estimates of the response of and difference between abrocitinib and dupilumab, along with the 95% confidence interval (no p-value), will be presented for each defined category of each subgroup. For the binary endpoints, analyses will be performed using normal approximation without any adjustments for baseline disease severity.

The primary purpose of the subgroup analyses is to check for consistency and robustness of results across subgroups, to make sure overall results are not being driven by some subset of participants.

Graphical display (eg, forest plots) of the differences between treatment groups will be presented. There is no intention to have any specific inference within subgroups.

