6.3. Measures to Minimize Bias: Randomization and Blinding

6.3.1. Allocation to Study Intervention

Allocation of participants to treatment groups will proceed through the use of an IRT system (interactive Web-based response [IWR]). The block randomization method will be used, and participants will be stratified by baseline disease severity (IGA = 3 vs. IGA = 4). The site personnel (study coordinator or specified designee) will be required to enter or select information including but not limited to the user's identification (ID) and password, the protocol number, and the participant number. The site personnel will then be provided with a treatment assignment, randomization number, and dispensable unit (DU) or container number when study intervention is being supplied via the IRT system. The IRT system will provide a confirmation report containing the participant number, randomization number, and DU or container number assigned. The confirmation report must be stored in the site's files.

Study intervention will be dispensed at the study visits summarized in the [SoA](#).

Returned study intervention must not be re-dispensed to the participants.

The study-specific IRT reference manual and IP manual will provide the contact information and further details on the use of the IRT system.

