2.2. Study Design

This is a randomized, double-blind, double-dummy, active controlled, multi-center study to assess the efficacy and safety of abrocitinib 200 mg QD compared with dupilumab (administered per label guidelines) in adult participants on background topical therapy, with moderate to severe AD. The treatment duration is 26 weeks. A total of approximately 600 participants will be enrolled from approximately 220 sites globally. There are primary efficacy assessments at Week 2 and Week 4, and a key secondary efficacy assessment at Week 16. Efficacy and safety endpoints will be assessed throughout the entire study. Participants who complete the study through the Week 26 visit and are deemed eligible will enter the long-term extension (LTE) Study B7451015. A study design schematic is presented in [Figure 1](#).

Figure 1 Study Design Schematic

Study Treatments

- Group 1 (N=300): Abrocitinib 200 mg (2 x 100 mg tablets) administered orally QD and dupilumab-matching placebo administered by subcutaneous injection every other week (2 injections at baseline; to dummy the loading dose) from Day 1 to Week 26 (the last injection of dupilumab-matching placebo will occur at Week 24).
- Group 2 (N=300): Dupilumab 300 mg administered by subcutaneous injection every other week (with a loading dose of 600 mg at baseline) and abrocitinib-matching placebo administered orally QD from Day 1 to Week 26 (the last injection of dupilumab will occur at Week 24).

Rescue Therapy for Atopic Dermatitis

- After Week 4, if medically necessary, participants with intolerable AD symptoms may receive locally-approved rescue therapy, at the investigator’s discretion.
- Participants receiving topical or systemic rescue therapy may continue to receive study intervention concurrently. Participants receiving rescue therapy should continue study visits and assessments.

Sample Size Determination

A total sample of 600 participants, with 300 participants randomized to abrocitinib, 300 participants randomized to dupilumab (1:1 randomization) is planned. The proposed sample size provides adequate power for all superiority hypotheses, as follows:

Week 2: This sample size would provide at least 99% power to detect a difference assuming a difference of at least 25% in PP-NRS response between abrocitinib and dupilumab and the dupilumab response rate is 11% at Week 2.

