Week 4: This sample size will provide approximately 99% power to detect a difference assuming a difference of at least 15% in Week 4 EASI-90 between abrocitinib and dupilumab and the dupilumab response rate is 12%.

Week 16: This sample size will provide at least 99% power to show the difference is no more than 10% favoring dupilumab in EASI-90 at Week 16 (non-inferiority [NI] with a 10% margin), assuming the abrocitinib response rate is 53% and the dupilumab response rate is 43% at Week 16. This sample size will also provide approximately 70% power to demonstrate superiority of abrocitinib 200 mg QD to dupilumab as measured by EASI-90 response at Week 16.

While the power to detect a difference at the early time points of 2 and 4 weeks and non-inferiority at week 16 is strong implying a decrease sample size could be used, the power to demonstrate superiority at week 16 requires the larger number of participants. Superiority at week 16 is a valuable endpoint for the scientific community and prescribers justifying the larger sample size. In addition, the study design avoids exposing participants to the use of placebo, i.e., will be guaranteed treatment on 1 of the 2 active treatment arms, which allows for potential benefit for all participants included in the study.

The familywise Type I error rate (for testing the primary and key secondary endpoints) will be strongly controlled at 5% (2-sided) using a sequential multiple testing procedure outlined in [Section 5.1](#).

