5. GENERAL METHODOLOGY AND CONVENTIONS

5.1. Hypotheses and Decision Rules

The Type I error rate is set at 5% (two sided). The familywise Type I error rate (for testing the primary and key secondary endpoints) will be strongly controlled at 5% using a sequential testing approach.

The procedure will test all hypothesis sequentially. If one hypothesis is not rejected at the 5% level, then the statistical significance will be not claimed for the subsequent hypotheses testing. The procedure will first test superiority of PP-NRS4 response at Week 2 and then EASI-90 at Week 4 between abrocitinib and dupilumab by CMH test specified in the primary analysis. If both hypotheses are rejected, the procedure will continue to test the NI of EASI-90 at Week 16 between abrocitinib and dupilumab. The 95% CMH weighted confidence interval will be constructed for the response difference and NI will be declared if the lower bound of the confidence interval for the response difference (abrocitinib - dupilumab) is greater than -10%. If the non-inferiority is achieved, the procedure will continue to test superiority of EASI-90 at Week 16 between abrocitinib and dupilumab by CMH test specified in the analysis for the key secondary endpoint.

The following figure illustrates the procedure showing the sequence of the tests.

A sequential, step-down approach with the PP-NRS4 endpoint from Week 2 to earlier time points will be utilized as an additional family of hypothesis tests once statistical significance is demonstrated at Week 2. Specifically, further hypotheses of no difference in PP-NRS4 between abrocitinib and dupilumab will be assessed at Day 15, Day 14, Day 13, Day 12, ..., Day 2, in that order. Any hypotheses after the last Day for which the comparison is significant will not be considered statistically significant. All hypotheses in the sequence will be assessed at the 5% level of significance. Although this will not protect the Type-I error for the family of all possible comparisons, it will provide Type-I error protection for the family of PP-NRS4 comparisons over the first 2 weeks.

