The 95% confidence interval for the response rate will also be provided using Wald normal approximation (or the Clopper-Pearson exact method when there are no or all responders in one group).

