5.2.3. Analyses for Longitudinal Continuous Endpoints

Mixed-effect, repeated measures (MMRM) models will be used. The fixed effects of treatment, visit, treatment-by-visit interaction and baseline disease severity will be included. Visit will be modeled as a categorical covariate. Unstructured covariance matrix will be assumed for the model errors. Compound symmetry covariance matrix will be used if the model with unstructured covariance doesn't converge.

When modeling the change from baseline values, the variable for visit will start with the first post-baseline visit, and the actual baseline value will be included as a covariate. At each visit, estimates of least square mean (LSM) values and the LSM differences between treatment groups will be derived from the model. The corresponding p-values and 95% confidence intervals will also be derived from the model. Graphs will describe the LSM over time.

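### Subgroup differences (SAP 6.4) and single-arm rates (SAP 5.2.1) rely on Wald limits that under-cover in small cells or at rates near zero; score-type or exact limits and one baseline-adjusted supplementary analysis would be a cheap improvement

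*SAP*

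**What the plan says.** **Randomisation and main analysis.** Under Protocol 6.3.1, "participants will be stratified by baseline disease severity" (IGA 3 against IGA 4). SAP 5.2.1 carries that stratum into the CMH test and the CMH-weighted difference with normal-approximation limits. If a cell has no responders, the standard error of the difference uses 0.5/(n + 1) in place of the observed rate. There is no matching rule when every participant in a cell responds.

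**Subgroups.** SAP 6.4 lists eleven subgroup factors and states that binary "analyses will be performed using normal approximation without any adjustments for baseline disease severity". It presents intervals without p-values, gives the purpose as a check of consistency, and disclaims inference within subgroups. It does not say whether the zero-responder rule carries over.

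**Single-arm rates.** SAP 5.2.1 adds: "The 95% confidence interval for the response rate will also be provided using Wald normal approximation", with a switch to Clopper-Pearson only if none or all respond. SAP 6.2.2.1 applies the same section to PP-NRS4 on each of Days 2 to 15.

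**Baseline score.** For change-from-baseline models SAP 5.2.3 includes severity "and the actual baseline value will be included as a covariate". The binary analyses adjust for IGA severity alone. The supplementary GLMM in SAP 5.3.1 has neither severity nor baseline score.

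**Reference list.** SAP section 8 lists the Miettinen-Nurminen paper on comparing two rates, but no analysis in the SAP text uses the method.

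**The concern.** A forest plot conveys consistency through its intervals. If the limits in the smallest rows are too short, ordinary chance variation can look like a real departure from the overall result. Small rows are plausible here (age 65 and over, some race categories, weight above 100 kg), and nothing in the plan limits how small they may be. The silence about the zero-responder rule also means that two programmers following 6.4 could print different intervals from the same data.

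The single-arm limits raise a similar question in full-arm tables on the early PP-NRS4 days, when few participants may have responded.

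The baseline score is a separate matter of efficiency. PP-NRS4 is defined as a change from baseline: a participant who starts at 4 must reach 0, and one who starts at 10 need only reach 6. Protocol 9.2 justifies the sample size by the Week 16 superiority test, which is planned at only about 70% power, so unused baseline information is worth a look.

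**Working it through.** **Inputs.** "The Type I error rate is set at 5% (two sided"; 300 per arm ("300 participants randomized to dupilumab (1:1 randomization) is planned"). Planning rates, abrocitinib against dupilumab: 36% against 11% at Week 2 ("assuming a difference of at least 25% in PP-NRS response between abrocitinib and dupilumab and the dupilumab response rate is 11% at Week 2"); 27% against 12% at Week 4 ("assuming a difference of at least 15% in Week 4 EASI-90 between abrocitinib and dupilumab and the dupilumab response rate is 12"); 53% against 43% at Week 16 (SAP 2.2). Assumed, because the documents do not give them: subgroup cell sizes, 40% of participants severe, a 1% early response rate, and the prognostic strength of the baseline score.

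**1. The plan's own figure.** Week 16 superiority: SE = sqrt(0.53 × 0.47/300 + 0.43 × 0.57/300) = 0.0406. Power = Φ(0.10/0.0406 − 1.96) = 69.3%, or 68.9% with pooled variance. The stated figure of about 70% reproduces.

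**2. Coverage of the subgroup interval.** All pairs of binomial outcomes were enumerated. The limits are p1 − p0 ± 1.96 × sqrt(p1(1 − p1)/n + p0(1 − p0)/n), with 0.5/(n + 1) in the SE when a cell has no responders. Coverage in percent, Wald with the zero rule / Miettinen-Nurminen:

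| n per arm | Week 2 | Week 4 | Week 16 |
|---|---|---|---|
| 5 | 91.3 / 98.3 | 96.5 / 98.5 | 86.0 / 95.0 |
| 10 | 92.0 / 97.1 | 91.9 / 97.0 | 91.0 / 95.6 |
| 15 | 91.9 / 94.4 | 92.8 / 94.6 | 93.5 / 93.6 |
| 20 | 93.4 / 94.1 | 93.8 / 94.9 | 93.5 / 95.8 |
| 30 | 94.2 / 94.9 | 94.2 / 95.1 | 94.6 / 94.9 |
| 50 | 94.5 / 95.3 | 94.5 / 95.0 | 94.4 / 94.5 |

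Newcombe limits give 95.6-97.0% at 10 per arm and 95.4-95.5% at 20. At 300 per arm, Wald gives 94.7% (Week 16) and 94.9% (Week 4).

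**3. The zero rule.** At Week 4 with 5 per arm, the chance of no responders is 0.88^5 = 52.8% on dupilumab and 0.73^5 = 20.7% on abrocitinib, and 0.528 × 0.207 = 10.9% in both. In that last case an interval without the rule has zero width. Coverage is 96.5% with the rule and 80.0% without it. At 8 per arm it is 96.1% and 86.3%.

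**4. The omitted stratum.** Simulation with 40% severe, whole-subgroup size N, unadjusted against CMH-weighted Wald coverage:
- N = 20: Week 4, 91.9% against 94.8%; Week 16, 91.0% against 90.1%.
- N = 100: Week 4, 94.5% against 94.2%; Week 16, 94.3% against 94.1%.
- SD of the Week 16 estimate: 0.223 against 0.228 at N = 20, and 0.0573 against 0.0571 at N = 300.

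Restoring the stratum neither cures the under-coverage reliably nor improves precision noticeably.

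**5. Single-arm Wald, n = 300, true rate 1%.** With one responder, the upper limit is 0.00333 + 1.96 × sqrt(0.00333 × 0.99667/300) = 0.0099, which misses 0.01. With nine responders, the lower limit is 0.0107, which also misses. Zero responders goes to Clopper-Pearson and covers. Coverage = 1 − P(X = 1) − P(X ≥ 9) = 1 − 0.1486 − 0.0036 = 84.8%. The lower limit is negative for 1 to 3 responders: 0.1486 + 0.2244 + 0.2252 = 59.8% of samples.

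**6. Baseline adjustment at Week 16.** Power = Φ(0.10/(0.0406 × sqrt(1 − R²)) − 1.96). For R² of 2%, 5% and 10%, power goes from 69.3% to 70.2%, 71.5% and 73.8%. A separate simulation compared logistic standardisation on severity plus baseline score with the CMH-weighted difference. It assumed log-odds of 0.25, 0.5 and 0.75 per SD and a correlation of 0.5 with severity. Variance falls by 0.9%, 2.9% and 8.7%, and pooled-variance power goes from 68.9% to 69.3%, 70.2% and 72.9%. The gain over both checks runs from 69.3 − 68.9 = 0.4 to 73.8 − 69.3 = 4.5 points.

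**The case against.** The subgroup output is descriptive. SAP 6.4 has no p-values and disclaims inference, so no decision rule uses these limits. At 10 per arm the Week 16 Wald half-width already averages about 41 points, and few readers would take such a row as precise. All of this stands, and it is why the point is minor. It does not make a nominal 95% interval correct, and the interval is what the plot shows.

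The SAP is not wholly unprotected. It has the zero-responder rule and the Clopper-Pearson switch. The missing all-responder rule rarely matters at planning rates: 0.53^10 = 0.2% for 10 per arm at Week 16. Score limits are also not better everywhere; at 15 and 50 per arm for Week 16 they match Wald to within 0.1 point. And no document gives a 1% rate: the lowest planning rate is 11%, and the Day 2 to 15 comparisons between arms use the CMH test, not the single-arm limits. These points narrow the concern without removing it.

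A reader might infer that dropping the stratum in 6.4 causes the under-coverage. Step 4 does not support that, and for the severity subgroup itself the stratum is the subgroup. A reader might also infer from the MMRM comparison that the main binary analysis is wrong without a baseline score. It is not: CMH adjusts for the only randomisation factor and is valid, and the MMRM is a different model for a different estimand.

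**Conclusion.** The point holds in a limited form, as a minor improvement. Wald limits for subgroup differences lose about 3 to 4 points of coverage at 10 per arm, 1 to 2 points at 20, and less than 1 point from 30. At 5 per arm the result depends on the endpoint and on whether the zero rule applies, from 80.0% to 96.5%. All of these figures rest on assumed cell sizes.

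The single-arm shortfall at 1% is real arithmetic on an assumed rate, and it affects descriptive limits only. The gain from baseline adjustment depends on prognostic strength that the documents do not give; across the range tried it is about 0.4 to 4.5 points of Week 16 superiority power. The main difference intervals, the testing sequence and the non-inferiority decision are not called into question.

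**What to change.** - **SAP 6.4:** use Miettinen-Nurminen limits (already in the reference list) or Newcombe limits for every subgroup difference. Both handle cells with no responders or all responders, so no separate rule is needed. Stating a minimum cell size for display would also help.
- **SAP 5.2.1:** use Wilson or Clopper-Pearson limits for all single-arm rates, not only where none or all respond.
- **SAP 6.1 and 6.2.1:** add one supplementary analysis of each primary and key secondary endpoint, giving a risk difference adjusted for IGA stratum and baseline PP-NRS or EASI by standardised logistic regression. Keep it supplementary: Protocol 9.4 requires an amendment for major changes to the primary or key secondary analyses, and the likely gain does not justify replacing a valid estimator. The CMH analysis, the testing sequence and the 10-point margin stay unchanged.

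The cost is SAP wording and slightly more programming in standard software. Some small-subgroup intervals will be wider.
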